2.2 Design

A mixed experimental design of 2 (Stimulation type: anodal stimulation, sham stimulation) \times 2 (Learning strategy: retrieval practice, restudy) \times 2 (Retention interval: Immediate recall, Delayed recall) was employed. Stimulation type was a between-subjects variable, while learning strategy and testing time were within-subject variables. The dependent variables were the correct recall rate and Adjusted Ratio of Clustering (ARC) scores in the testing phase.

2.3 Devices and Materials

2.3.1 Devices

The direct current stimulation device powered by batteries used in this study was the Starstim system from NE (Neuroelectrics) company in Spain. All groups utilized the same

electrode montage, and the electrode placement followed the international 10-20 system for electroencephalography. The tDCS intervention employed 8 cm² circular sponge electrodes. The anode was placed over F3 (i.e., L-DLPFC) and the cathode over FP2 (i.e., right supraorbital area).

2.3.2 Materials

Thirty-four words from eight common semantic categories were selected as the learning materials. Among them, five words were chosen from each of the six categories (fruits, clothing, musical instruments, sports, stationery, media) as experimental items, while two words were selected from each of the remaining two categories (daily necessities, body organs) as filler items. These filler items were presented at the beginning and end of the learning list to control for primacy and recency effects, respectively.

The selection of experimental categories followed the following rules:(1)To control for the mutual influence between categories, relatively unrelated categories were chosen (the main control was the degree of association between categories and their knowledge domains, such as choosing between fruits and vegetables); (2)Two-character words with clear semantics were selected as sample words. The selection of sample words followed these rules: 1) Each sample word was a two-character word with clear semantics; 2) Each sample word had a different pronunciation [13].

Prior to the formal experiment, 20 schizophrenia patients were randomly selected as participants to assess the semantic familiarity and relevance of 30 pairs of category sample word pairs. Evaluation was conducted on a Likert five-point scale (1 indicating complete

unfamiliarity or no relation, and 5 indicating complete familiarity or very close relation). The results indicated that there were no significant differences between the familiarity ($M = 4.42$, $SD = 0.76$) and relevance ($M = 4.75$, $SD = 0.47$) of the retrieval practice list (fruits, clothing, instruments) and the familiarity ($M = 4.61$, $SD = 0.59$) and relevance ($M = 4.65$, $SD = 0.45$) of the restudy list (sports, stationery, media), $t(19) = -1.765$, $p = .094$, 95% CI [-0.41, 0.03], $t(19) = 1.344$, $p = .195$, 95% CI [-0.05, 0.25].

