2.4 Procedure

Treatment was administered by two examiners, and after a total of 10 sessions over 5 consecutive days, a final group of 52 patients participated in the learning and testing phase. Among them, 27 received anodal stimulation, while 25 received sham stimulation. Each participant of each stimulation type was involved in both learning conditions, meaning that all participants completed both retrieval and restudy learning and testing (experimental procedure in **Figure 1**).

(1) Stimulation phase

In the anodal group, the anode was placed over the left DLPFC (F3), and the cathode was placed over the contralateral supraorbital area (FP2). A direct current of 2mA was applied for 20 minutes during each stimulation session. Stimulation was conducted twice a day, at 9 a.m. and 2 p.m., for 5 consecutive days, totaling 10 sessions. In the sham group, the stimulation parameters, including the stimulation site and duration, were identical to those of the anodal group. However, during the 10-second ramp-up and ramp-down periods before and after stimulation, patients were unaware that the current was turned off.

(2) Learning phase

The experimental procedure followed the classic retrieval practice paradigm, which included a learning phase and a final test phase.

During the experiment, participants were informed that they would learn two lists of words. Subsequently, they might either learn the words again or complete a list recall test, and will be given a final test shortly thereafter. The learning of the retrieval practice list and the restudy list was conducted in a randomly balanced manner. Each word was presented for 5 seconds, with a 500-millisecond interval between words. To avoid providing secondary retrieval cues between examples, all words were shuffled pseudo-randomly within categories. Each list contained 17 words, consisting of 5 examples from each of the 3 experimental categories (15 experimental examples, 2 filler examples). The first and last words presented in each list were filler words, thus controlling for the primacy and recency effects on memory.

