For the retrieval practice list, participants underwent two learning sessions and two retrieval sessions (S-T-S-T). During retrieval, participants were instructed to write down all the words they had just remembered within 5 minutes. For the restudy list, participants underwent four study sessions (S-S-S-S). Between each learning cycle, participants completed a 3-minute simple arithmetic task (dispersed attention task).

(3) Testing phase

Immediate Test: Participants were instructed to recall as many words as possible from the learned lists within 10 minutes after completing all learning tasks.

Delayed Test: Participants were informed to recall as many words as possible from the

learned lists within 10 minutes 24 hours later.

[figure not shown]

Figure 1. Experiment procedure.

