2.5 Date scoring & analysis

The experimental results were processed using SPSS 26.0. The correct recall rate of word lists was calculated for each subject by the experimental assistant. Then, Free recall organization was measured by the Adjusted Ratio of Clustering (ARC) scores [14,15]. ARC scores range from 1 to 1. A 0 score indicates a level of clustering similar to what would be expected by chance, and a score of 1 implies perfect clustering. Negative values of ARC scores mean atypical and uninterpretable recall patterns[16]. For that reason, negative scores were excluded from analyses.

A mixed-design analysis of variance (ANOVA) was conducted to compare the correct recall rates and ARC clustering scores between the two learning strategies under two stimulation conditions. All statistical tests were performed at a significance level of 0.05, and post-hoc comparisons were adjusted using Bonferroni correction. Effect sizes were reported using partial eta-squared (η_p^2 ; ANOVAs).

3. Study Status

Record Verification: July 2024

Overall Status: Completed

Study Start: July 24, 2023 [Actual]

Primary Completion: January 30, 2024 [Actual]

Study Completion: April 15, 2024 [Actual]

List of abbreviations

tDCS transcranial direct current stimulation

L-DLPFC left dorsolateral prefrontal cortex

VLPFC ventrolateral prefrontal cortex

ARC Adjusted Ratio of Clustering

References

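### As printed, each learning strategy has its own fixed word categories, so the retrieval-versus-restudy effect cannot be separated from list content

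*Protocol*

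**What the plan says.** Section 2.2 makes learning strategy a within-subject factor, and section 2.4 has every participant complete both strategies.

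Section 2.3.2 gives each strategy its own content: "the retrieval practice list (fruits, clothing, instruments") and "the restudy list (sports, stationery, media"). It reports that 20 patients rated the two lists and that neither familiarity nor relevance differed significantly.

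Section 2.4 attaches the schedules to the same named lists: "For the retrieval practice list, participants underwent two learning sessions and two retrieval sessions (S-T-S-T") and "For the restudy list, participants underwent four study sessions (S-S-S-S"). Its only statement on balancing is: "The learning of the retrieval practice list and the restudy list was conducted in a randomly balanced manner".

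Section 2.5 plans a mixed-design ANOVA to "compare the correct recall rates and ARC clustering scores between the two learning strategies under two stimulation conditions". It names no list or category term. Section 3 gives "Overall Status: Completed".

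**The concern.** If every patient retrieves one set of categories and restudies the other, strategy and list content are the same variable. Any difference between the two sets in how easily their words are recalled, or how readily they cluster, goes straight into the strategy effect. No later analysis can remove it, because a list term is not estimable under fixed assignment.

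At stake are the strategy main effect and the within-arm strategy contrasts, for recall and for ARC. A finding that retrieval practice helps patients, or that it helps under one type of stimulation, could reflect easier categories. A true benefit could equally be hidden by harder ones.

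**Working it through.** **1. What is tied to what.** As printed, retrieval practice = S-T-S-T = fruits, clothing, instruments, and restudy = S-S-S-S = sports, stationery, media. Take a design matrix for 27 anodal and 25 sham patients with two lists each, and columns for intercept, arm, strategy, list, arm × strategy and arm × list. The strategy and list columns correlate at 1.00 and the rank is 4 of 6. With content swapped for alternate patients within each arm, the rank is 6 of 6 and the correlation is 0.04; it is not zero only because 27 and 25 are odd.

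**2. The protocol's list check, reproduced.** SE = difference / t; 95% CI = difference ± 2.093 × SE (19 df).

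| Rating | Difference (retrieval − restudy) | SE | 95% CI | p | Printed |
|---|---|---|---|---|---|
| Familiarity | 4.42 − 4.61 = −0.19 | 0.19/1.765 = 0.108 | −0.415 to 0.035 | 0.094 | −0.41 to 0.03, .094 |
| Relevance | 4.75 − 4.65 = +0.10 | 0.10/1.344 = 0.074 | −0.056 to 0.256 | 0.195 | −0.05 to 0.25, .195 |

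The printed figures agree within rounding, but they do not establish equivalence. The 90% intervals (± 1.729 × SE) are −0.376 to −0.004 and −0.029 to 0.229. Two one-sided tests would therefore support equivalence only for margins above 0.38 and 0.23 points. The standardised paired differences are 0.39 and 0.30 SD, and 20 raters give about 39% and 25% power to detect differences of that size. The two ratings point in opposite directions, so they do not indicate which way a list effect would run. No comparison of the lists on recall or clustering is reported.

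**3. Size for recall (illustrative).** Assumptions: the within-person strategy difference in recall rate has SD 0.15–0.20; the 15 experimental words per list are the denominator; there is no true strategy effect.

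- SE = SD/√52 = 0.0208 to 0.0277.
- The critical difference is 2.009 × SE = 0.042 to 0.056, which is 0.63 to 0.84 of 15 words.
- The rejection rate comes from the noncentral t (50 df) with noncentrality (words/15)/SE. For one word: 0.0667/0.0208 = 3.20, or 0.0667/0.0277 = 2.40.

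| List difference | Significant strategy main effect (nominal 5%) |
|---|---|
| 0.25 word | 9–12% |
| 0.5 word | 22–35% |
| 1 word | 65–88% |

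For an unadjusted contrast within one arm (n = 27, 26 df, or n = 25, 24 df), one word gives 36–60%.

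**4. What is protected.** Both arms receive the same lists under the same strategies, so an additive list effect cancels from the stimulation × strategy interaction. In 40,000 simulated trials per setting (27 v 25), a list difference of 0.5 or 1 word left its error rate at 4.8–5.1%. If effects add on the logit scale instead, take a one-word list effect and a 10-point stimulation effect (both assumed). The interaction on the rate scale is then between +0.001 and −0.031 for base recall of 0.4 to 0.8. Its SE is SD × √(1/27 + 1/25) = 0.042 to 0.056. The error rate is 5–6% at base recall 0.4–0.6 and 8–11% at 0.8.

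**The case against.** **The balancing sentence could cover content.** The name of a list might mean whichever list a patient received under that strategy, and Figure 1, which shows the procedure, is not available here. The doubt is real, but order is the more natural reading, because the sentence speaks of lists that already carry a strategy label. If categories were swapped, section 2.3.2 is wrong to give each named list a fixed content. The text needs correcting on either reading.

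**The stated aim concerns stimulation.** Patients were randomised to stimulation, and the question of combining tDCS with retrieval practice rests mainly on the stimulation effect and the interaction. This stands and limits the damage. Section 2.5 nevertheless plans the strategy comparison explicitly.

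**The lists were matched.** Words were selected by rule, mean ratings lie between 4.42 and 4.75 on a five-point scale, and the protocol claims only no significant difference, not equivalence. Matching makes a large list effect less likely, but it leaves the aliasing in place and did not address recall or clustering.

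**The magnitude is assumed.** This is correct. At SD 0.30, one word gives 35% and a quarter word 7%. The within-arm figures also omit the planned Bonferroni correction; if two within-arm contrasts share it, 36–60% becomes 25–48%. The aliasing itself needs no assumption.

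**Conclusion.** The point holds for the protocol as printed. The strategy main effect and the within-arm strategy contrasts estimate strategy plus list content, for recall and ARC, and the 20-patient rating does not rule out a list effect that matters. The percentages rest on an assumed SD and assumed list differences, cover recall only, and show what could happen rather than what did.

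The stimulation main effect is sound on this point. The stimulation × strategy interaction is sound against an additive list effect, but it cannot be told apart from stimulation acting differently on the two category sets, and it is mildly exposed near ceiling. Strategy × interval is affected only if the lists differ in forgetting or through similar scale effects.

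Confidence is moderate, because the balancing sentence is loose and the procedure figure is not shown.

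**What to change.** **Completed trial.** State whether categories were exchanged between strategies.

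- If they were, reconcile sections 2.3.2 and 2.4, say how the exchange was done, and add list version to the ANOVA as a between-subject factor.
- If they were not, describe the strategy main effect and within-arm strategy contrasts as strategy plus list. Rest conclusions on the stimulation main effect and the stimulation × strategy interaction, with the caveat on list-specific stimulation effects and ceiling.

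The cost is some rewording and, if lists were exchanged, one extra model factor.

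**Any repeat.** Define List A and List B by content. In half of each stimulation arm use A for retrieval and B for restudy, and the reverse in the other half, crossed with learning order. Include list version in the model. This needs a second presentation file and one allocation column, with no extra patients, visits or words.

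With cells of 14/13 and 13/12, the SE of the strategy effect rises by a factor of 1.0007 and the t quantile (48 v 50 df) by 1.0010, so the confidence interval widens by about 0.2%. With a one-word list difference, the simulated type I error for strategy is then 5.1% (SD 0.15) and 4.9% (SD 0.20).

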2.4 Procedure

Treatment was administered by two examiners, and after a total of 10 sessions over 5 consecutive days, a final group of 52 patients participated in the learning and testing phase. Among them, 27 received anodal stimulation, while 25 received sham stimulation. Each participant of each stimulation type was involved in both learning conditions, meaning that all participants completed both retrieval and restudy learning and testing (experimental procedure in **Figure 1**).

(1) Stimulation phase

In the anodal group, the anode was placed over the left DLPFC (F3), and the cathode was placed over the contralateral supraorbital area (FP2). A direct current of 2mA was applied for 20 minutes during each stimulation session. Stimulation was conducted twice a day, at 9 a.m. and 2 p.m., for 5 consecutive days, totaling 10 sessions. In the sham group, the stimulation parameters, including the stimulation site and duration, were identical to those of the anodal group. However, during the 10-second ramp-up and ramp-down periods before and after stimulation, patients were unaware that the current was turned off.

(2) Learning phase

The experimental procedure followed the classic retrieval practice paradigm, which included a learning phase and a final test phase.

During the experiment, participants were informed that they would learn two lists of words. Subsequently, they might either learn the words again or complete a list recall test, and will be given a final test shortly thereafter. The learning of the retrieval practice list and the restudy list was conducted in a randomly balanced manner. Each word was presented for 5 seconds, with a 500-millisecond interval between words. To avoid providing secondary retrieval cues between examples, all words were shuffled pseudo-randomly within categories. Each list contained 17 words, consisting of 5 examples from each of the 3 experimental categories (15 experimental examples, 2 filler examples). The first and last words presented in each list were filler words, thus controlling for the primacy and recency effects on memory.

For the retrieval practice list, participants underwent two learning sessions and two retrieval sessions (S-T-S-T). During retrieval, participants were instructed to write down all the words they had just remembered within 5 minutes. For the restudy list, participants underwent four study sessions (S-S-S-S). Between each learning cycle, participants completed a 3-minute simple arithmetic task (dispersed attention task).

(3) Testing phase

Immediate Test: Participants were instructed to recall as many words as possible from the learned lists within 10 minutes after completing all learning tasks.

Delayed Test: Participants were informed to recall as many words as possible from the

learned lists within 10 minutes 24 hours later.

[figure not shown]

Figure 1. Experiment procedure.

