2.1 Participants

55 schizophrenic patients expected to be recruited from the mental health center. All patients must sign an informed consent form.

Patients with schizophrenia were diagnosed and assessed by two chief psychiatrists. Neuropsychological background tests included the Montreal Cognitive Assessment (MoCA)[11] for general cognitive function and the Positive and Negative Syndrome Scale (PANSS)[12]. A parallel-group, single-blind study design was used to assign subjects to the two stimulus types using a stratified randomization method based on baseline Montreal Cognitive Assessment performance. The characteristics of the participants are presented in Table 1, showing no significant differences in participant characteristics between the two stimulation types groups.

Patients with schizophrenia were included based on the following criteria: (1) meeting the diagnostic criteria for schizophrenia according to the Diagnostic and Statistical Manual of Mental Disorders, Fifth Edition (DSM-5); (2) aged 18 years or older, regardless of gender, with an educational level of elementary school or above; (3) all patients received stable-level

antipsychotic medication treatment, were in a stable phase of disease treatment, able to understand the testing requirements, and cooperated to complete all research tasks; (4) no history of neurological disorders or other serious physical illnesses, and no history of intellectual disability; (5) no color blindness, color weakness, or other color vision impairments, with normal vision or corrected vision.

Exclusion criteria were as follows: (1) clear cognitive impairment caused by somatic or cerebral organic lesions, such as cerebrovascular diseases, traumatic brain injury, etc; (2) individuals with mental disorders caused by substance dependence or abuse, or the use of psychoactive substances; (3) history of brain injury or other central nervous system-related organic diseases; (4) individuals at significant risk of suicide or harming others; (5) participation in similar experiments in the past 30 days prior to baseline.

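### The single-blind design masks patients only and does not keep the two examiners who deliver real or sham current from running the same patient's learning and recall sessions, which leaves the stimulation effect open to tester influence

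*Protocol*

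**What the plan says.** Section 2.1 sets the level of masking: "A parallel-group, single-blind study design was used to assign subjects to the two stimulus types". It does not name the masked party. The only masking described is in section 2.4, under the stimulation phase, where for the sham group "patients were unaware that the current was turned off".

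On delivery, section 2.4 says "Treatment was administered by two examiners". Each patient has ten sessions over five days, after which "a final group of 52 patients participated in the learning and testing phase". Of these, "27 received anodal stimulation, while 25 received sham stimulation".

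The learning and testing phases are written in the passive voice, with no staff named. For the practice recalls, "participants were instructed to write down all the words they had just remembered within 5 minutes". For the immediate test, "Participants were instructed to recall as many words as possible from the learned lists within 10 minutes after completing all learning tasks"; the test 24 hours later has the same time limit. Section 2.5 gives the calculation of recall rates to an assistant, without saying whether that person knows the arm. Nothing in the document separates the person who delivers the current from the person who runs the recall sessions.

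**The concern.** Both dependent variables in section 2.2, the correct recall rate and the clustering score, come from free recall. How much a patient produces depends partly on how firmly the instruction is given, whether someone who stops early is encouraged to go on, and when the session is ended. A tester who knows the arm can influence all three without intending to. Scoring the output blind afterwards does not help, because the influence is already in the words recalled.

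Stimulation type is the between-subjects factor, so any arm-related difference in test administration is confounded with the effect of stimulation. No later analysis of the recall scores can separate the two. Masking and the assignment of test staff are matters of trial conduct that belong in the protocol, so the fact that no SAP is at hand does not account for the gap.

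**Working it through.** The protocol gives no recall SD and no power calculation, so there is no figure of its own to reproduce. The check has two parts: which contrasts are exposed, and how small a lean would matter.

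**Exposure of each contrast.** Let *b* be an average gain in anodal patients from encouragement at a final test, equal on both lists. Let *p* be an average gain on the retrieval-practice list from encouragement during its two practice recalls. The restudy list has no practice recalls (S-S-S-S against S-T-S-T).

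- Anodal minus sham, retrieval-practice list: *b* + *p*
- Anodal minus sham, restudy list: *b*
- Stimulation effect averaged over the lists: [(*b* + *p*) + *b*]/2 = *b* + *p*/2
- Stimulation-by-strategy interaction: (*b* + *p*) − *b* = *p*

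The stimulation effect takes the whole of *b*. In the interaction *b* cancels, and what remains is mainly arm-dependent prompting in the practice recalls, or prompting that favours one list. Retrieval practice against restudy is compared within patients, so *b* cancels there too within each patient, and that contrast is less exposed.

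**Illustrative size for the stimulation effect.**

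- From the protocol: arms of 27 and 25; 15 scored words per list; significance level 0.05, taken as two-sided because sidedness is not stated.
- Assumed: a between-patient SD of 15, 20 or 25 percentage points for the recall score; an average lean in one arm of half a word (0.5/15 = 3.33 points) or one word (1/15 = 6.67 points) per list; no true effect.
- Standard error: SE = SD × √(1/27 + 1/25) = SD × 0.2776.
- Rejection rate, normal approximation: Φ(d/SE − 1.96) + Φ(−d/SE − 1.96), where d is the lean.

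| Assumed SD | SE | d/SE, half a word | Error rate | d/SE, one word | Error rate |
|---|---|---|---|---|---|
| 15 | 4.16 | 0.80 | 0.126 | 1.60 | 0.360 |
| 20 | 5.55 | 0.60 | 0.092 | 1.20 | 0.225 |
| 25 | 6.94 | 0.48 | 0.077 | 0.96 | 0.161 |

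A noncentral t calculation with 27 + 25 − 2 = 50 degrees of freedom gives 0.349, 0.218 and 0.156 for one word, so the approximation makes little difference. With no lean the rate stays at 0.05.

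**The case against.** The strongest reply is that the point rests on silence. No sentence says that the treating examiners ran the tests, knew the arm or prompted anyone. Their knowledge of the arm is inferred from the single-blind label and one sentence about sham patients. Other staff exist (an assistant who scores, two psychiatrists who diagnose) and might have run the sessions. This stands, and it limits the point to an unprotected risk. It does not remove the point, because the protocol states its level of masking and describes masking for patients only.

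The procedure is also partly standardised: words appear for 5 seconds at fixed intervals, recall is capped at 5 or 10 minutes, and practice recall is written (the response mode of the final tests is not stated). This narrows the room for influence, but a time cap does not control encouragement or an early stop.

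A reader might infer that any encouragement of anodal patients would imitate the synergy the trial is looking for. The design does not support that: equal encouragement at the final tests cancels in the interaction, as shown above. A reader might also infer that splitting the examiners' roles would prevent the bias. It would do so only while the tester stays unaware of the arm, and two colleagues exchanging roles across patients could disclose it. Patients could also guess their own arm.

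Finally, section 3 lists the study as completed and the document is dated after completion. A change to the staffing rota may therefore no longer be possible, and writing one in as though it had been followed would be wrong. That stands and shapes the fix.

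**Conclusion.** The point holds as an unprotected risk of bias. The plan commits to single-blinding, masks patients only, and leaves the treating examiners free to run effort-dependent recall sessions for the patients they treated. The between-subjects stimulation effect is the contrast most at risk. The interaction is exposed mainly through the two practice recalls, and the comparison of retrieval practice with restudy less so.

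Under the assumed SDs, an average lean of half a word in 15 would take the 5% error to about 8 to 13%, and one word to about 16 to 36%. Both the SD and the lean are assumptions. The figures show how small an influence would matter in arms of this size. They are not evidence that one occurred, and no rate is given for the interaction. The point deserves action because the stimulation claim depends on this contrast. Confidence is medium because the document does not say who ran the tests.

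**What to change.** In section 2.4, state that for a given patient one of the two existing examiners delivers all stimulation. The other, kept unaware of that patient's allocation and told not to discuss it, runs the learning, immediate and 24-hour sessions from a fixed script without extra prompting. Roles may alternate across patients.

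Because the trial is listed as completed, write this only if it was done. If it was not, state for each patient whether the person who ran the tests also delivered the stimulation or knew the arm. Where so, limit the conclusion on the stimulation effect by saying that test administration was unmasked. Say also whether the assistant who scored recall knew the arm.

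As a design, the cost is a rota and a short script, with no extra staff if the two examiners can cover both roles; the downside is less flexible scheduling over the treatment and test days. As a disclosure for the completed trial, the cost is a check of who tested whom and a few sentences in the report.

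### The randomly balanced learning order of the two word lists is left out of the stated ANOVA, so any order effect is counted as error in the strategy and stimulation × strategy tests: a loss of precision, without material bias

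*Protocol*

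**What the plan says.** Section 2.4 of the protocol has every patient learn under both strategies and says of the two lists: "The learning of the retrieval practice list and the restudy list was conducted in a randomly balanced manner". Section 2.3.2 assigns fruits, clothing and instruments to the retrieval list and sports, stationery and media to the restudy list. The pairing of words with strategy is therefore fixed, and order is what remains to be balanced.

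Section 2.2 sets out a 2 × 2 × 2 design: "Stimulation type was a between-subjects variable, while learning strategy and testing time were within-subject variables". Section 2.5 describes a mixed-design ANOVA to "compare the correct recall rates and ARC clustering scores between the two learning strategies under two stimulation conditions", and adds: "All statistical tests were performed at a significance level of 0.05". Neither section mentions learning order. Of the patients who reached the learning and testing phase, "27 received anodal stimulation, while 25 received sham stimulation".

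The immediate test comes after all learning is finished, and the delayed test 24 hours later.

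**The concern.** With two lists per patient in balanced order, the learning part is laid out like a two-period crossover. Strategy, and its interaction with stimulation, are tested on each patient's retrieval-minus-restudy difference. If the list learned first is recalled worse than the list learned second, that difference is pushed down in patients who began with retrieval and up in those who began with restudy. Balance cancels the average of these shifts but not their spread. A model without order treats the spread as unexplained variation between patients.

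An order effect is plausible. The immediate test follows all learning, so if one list's cycle is completed before the other begins, the first list waits through the whole second block and meets interference from another 17 words. At stake is the power of the strategy test and of the stimulation × strategy test. The latter is the question the trial was set up to answer, and 52 patients leave little to spare.

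**Working it through.** The protocol gives no power calculation, SD, effect size or order effect, so there is no stated figure to reproduce. The inputs below are marked by source.

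**From the protocol:** 27 anodal and 25 sham patients; two-sided 0.05; 17 words per list (15 experimental), 5 s each with 0.5 s between words; four study passes for restudy; two study passes and two recalls of up to 5 min for retrieval; a 3-min arithmetic task between cycles.

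**Assumed:** SD of the within-patient difference s = 0.20 on the recall-rate scale; interaction 0.15; gap g between lists learned first and second of 0.05 or 0.10 (0.05 × 15 = 0.75 word; 0.10 × 15 = 1.5 words); one list's cycle finished before the other begins.

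**Step 1: how much longer the first list waits.**
- One study pass: 17 × 5 + 16 × 0.5 = 93 s.
- Restudy block: 4 × 93 + 3 × 180 = 912 s = 15.2 min.
- Retrieval block, at most: 2 × 93 + 2 × 300 + 3 × 180 = 1,326 s = 22.1 min.

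The first list therefore waits about 15 min longer if restudy comes second, and up to 22 min longer if retrieval comes second.

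**Step 2: error variance.** Order shifts the difference by +g or −g. With about half the patients in each order, the error variance is s² + g² without an order term and s² with one.
- g = 0.05: (0.0400 + 0.0025)/0.0400 = 1.06.
- g = 0.10: (0.0400 + 0.0100)/0.0400 = 1.25.

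**Step 3: power for the interaction.** Standard error = SD × √(1/27 + 1/25) = SD × 0.2776; noncentrality = 0.15/standard error; noncentral t with 50 df (49 with order).

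| Gap | SD without order | Noncentrality | Power without order | Power with order |
|---|---|---|---|---|
| 0 | 0.200 | 2.70 | 75.5% | 75.5% |
| 0.05 | 0.206 | 2.62 | 73% | 75% |
| 0.10 | 0.224 | 2.42 | 66% | 75% |

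**Step 4: sensitivity to the SD.** For s from 0.15 to 0.30, variance inflation runs from 1.11 down to 1.03 at g = 0.05, and from 1.44 down to 1.11 at g = 0.10.

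**Step 5: the same in SD units.** Take an effect that has 80% power when there is no order effect. Omitting order leaves 79.6%, 77.6%, 70.7%, 61.1% and 50.8% power for g/s = 0.1, 0.25, 0.5, 0.75 and 1.0. A simulation with order assigned by simple randomisation (20,000 runs per setting) agrees, with the type I error near 0.05. If order is balanced as closely as the numbers allow, the strategy test at g/s = 0.5 has 72.5% power and a true type I error of 0.027: it becomes conservative, not invalid. With order in the model, simulated power stays at about 79 to 81% throughout.

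**Step 6: bias.** Arms of 27 and 25 are both odd, so order cannot be exactly balanced within either. With one patient over in each arm, in opposite directions, the interaction estimate moves by g × (1/27 + 1/25) = 0.077g. For g = 0.10 this is 0.008, against the assumed interaction of 0.15.

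**The case against.** **It is SAP detail.** Terms for counterbalancing are often left to an analysis plan, and the sentence in section 2.5 is a summary: it does not even repeat retention interval. This lowers the weight of the point but does not remove it. The protocol itself lays out the factor structure, and order is absent from it. A separate plan, not seen here, may already include the term.

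**The size is assumed.** This stands. The lag argument also bears mainly on the immediate test. At 24 hours, 15 to 22 min is only about 1 to 1.5% of the interval, and the strategy and interaction tests average over both intervals. A gap of 0.10 at the immediate test and none at 24 hours averages to 0.05, which is the smaller case. The 66% figure needs the full gap at both tests.

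**The sequence is inferred.** This also stands. The text does not say that one list is finished before the other starts, and Figure 1 is not shown.

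**Readings that go too far.** A reader might infer that an order term would also correct the unequal lags. It would not. Over balanced orders, the restudy list waits on average (22.1 − 15.2)/2 ≈ 3.5 min longer than the retrieval list. That follows from the unequal block lengths, is confounded with strategy, and stays in the estimate with or without an order term. A reader might also infer that the reported strategy effects are biased or that false positives are more likely. Balance protects the estimates apart from the small remainder in step 6, and the type I error is at or below 0.05.

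**Conclusion.** The point holds as one of precision. Order was randomly balanced, the stated model omits it, and any order effect on the within-patient difference then inflates the error term for strategy and stimulation × strategy. On the assumed SD and interaction, the loss in interaction power is about 2 to 3 percentage points for a gap of 0.05. It is about 9 to 10 points for a gap of 0.10 that persists to 24 hours, and nil if order has no effect. The smaller case is the better illustration if the lag is the only source of the order effect. A simple order shift does not affect the between-patient main effect of stimulation. No size is derived here for ARC. The conclusion rests on reading the balancing as balancing of order; the lag argument rests also on the two lists being learned one after the other. This is a minor to moderate point, worth making because the remedy is nearly free.

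**What to change.** Add learning order (retrieval list first or restudy list first) as a between-subjects factor, with its order × strategy term, to the ANOVAs for recall rate and ARC. The order × strategy term is the one that takes the order effect out of the error. State whether order was balanced within each stimulation arm, and whether one list's cycle was completed before the other began.

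The cost is one error degree of freedom (50 to 49). With no order effect, power stays at about 75.5%. Even a full-factorial model, which uses two degrees of freedom, leaves 75.4%. The change needs each patient's learning order to be on record, which the protocol does not confirm.

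Section 3 gives the study as completed, so the term should be declared as added after the fact, and the results shown beside those of the stated model. The average lag difference between strategies should be noted separately as a limitation, since this change does not address it.
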